## 11.1.2 Progression-Free and Overall Survival

Overall Survival: Overall Survival (OS) is defined as the time from randomization (or registration) to death due to any cause, or censored at date last known alive.

*Progression-Free Survival*: Progression-Free Survival (PFS) is defined as the time from randomization (or registration) to the earlier of progression or death due to any cause. Participants alive without disease progression are censored at date of last disease evaluation.

*Time to Progression*: Time to Progression (TTP) is defined as the time from randomization (or registration) to progression, or censored at date of last disease evaluation for those without progression reported.

# 11.1.3 Response Review

For purposes of data analysis and reporting, responses on this trial will be centrally assessed through the Tumor Imaging Metrics Core at DF/HCC.

# 12. DATA REPORTING / REGULATORY REQUIREMENTS

Adverse event lists, guidelines, and instructions for AE reporting can be found in Section 7.0 (Adverse Events: List and Reporting Requirements).

# 12.1 Data Reporting

## 12.1.1 Method

The Office of Data Quality (ODQ) will collect, manage, and perform quality checks on the data for this study.

# 12.1.2 Responsibility for Data Submission

Investigative sites are responsible for submitting data and/or data forms to the Office of Data Quality (ODQ) in accordance with DF/HCC policies.

# 12.2 Data Safety Monitoring

The DF/HCC Data and Safety Monitoring Committee (DSMC) will review and monitor toxicity and accrual data from this study. The committee is composed of medical oncologists, research nurses, pharmacists and biostatisticians with direct experience in cancer clinical research. Information that raises any questions about participant safety will be addressed with the Sponsor-Investigator and study team.

The DSMC generally reviews each protocol up to four times a year with the frequency determined by the outcome of previous reviews. Information to be provided to the committee

may include: up-to-date participant accrual; current dose level information; DLT information; all grade 2 or higher unexpected adverse events that have been reported across all sites; summary of all deaths occurring within 30 days of intervention for Phase I or II protocols; for gene therapy protocols, summary of all deaths while being treated and during active follow-up; any response information; audit results, and a summary provided by the study team. Other information (e.g. scans, laboratory values) will be provided upon request.

## 12.3 Multi-Center Guidelines

This protocol will adhere to DF/HCC Policy MULTI-100 and the requirements of the DF/HCC Multi-Center Data and Safety Monitoring Plan. The specific responsibilities of the Sponsor-Investigator, Coordinating Center, and Participating Institutions and the procedures for auditing are presented in Appendix B.

## 13. STATISTICAL CONSIDERATIONS

This is an open label phase II clinical trial of ipilimumab with or without nivolumab in patients with relapsed/refractory classical Hodgkin lymphoma. The trial is designed to assess the efficacy of ipilimumab with or without nivolumab in patients with relapsed/refractory Hodgkin lymphoma.

## 13.1 Study Design/Endpoints

Primary Endpoint

• Best ORR (Lugano criteria)

# Secondary Endpoints

- Best ORR, PRR, CRR assessed by PET/CT (using Lugano criteria and LYRIC criteria) after ipilimumab monotherapy
- Best ORR, PRR, CRR assessed by PET/CT (using Lugano criteria and LYRIC criteria) after ipilimumab and nivolumab combination therapy
- DOR (using Lugano criteria and LYRIC criteria) for patients receiving ipilimumab maintenance
- DOR (using Lugano criteria and LYRIC criteria) for patients receiving ipilimumab and nivolumab combination therapy
- PFS and OS (Lugano criteria and LYRIC criteria)
- Safety
- Above endpoints, stratified by best response to PD-1 mAb (non-responder versus responder)

# Correlative Endpoints

- To determine if features of the cHL TME are associated with response or resistance to study treatment
- To determine if early reduction in ctDNA is associated with improved PFS.

• To characterize the genetic bases of immune evasion and correlate these alterations with responses to therapy

# 13.2 Sample Size, Accrual Rate and Study Duration

We anticipate that 13 patients will be enrolled in this phase II trial. We estimate that patients will be enrolled over a 30-month period. Up to 3 months of additional follow-up will be required to observe a participant's response. Therefore, we anticipate analysis of primary endpoints after a total of 33 months. The end of the trial will occur when all patients have stopped study treatment (due to progression, withdrawal of consent, adverse events, etc).

Table 8 - Accrual Targets										
Ethnic Category		Sex/Gender								
		Females			Males			Total		
Hispanic or Latino	1		+	1			2			
Not Hispanic or Latino	5		+	6		=	11			
Ethnic Category: Total of all subjects		(A1)	+	7	(B1)		13	(0	C1)	
Racial Category										
American Indian or Alaskan Native	0		+	0			0			
Asian	0		+	1			1			
Black or African American	1		+	0			1			
Native Hawaiian or other Pacific Islander	0		+	0		=	0			
White	6		+	5			11			
Racial Category: Total of all subjects	7	(A2)	+	6	(B2)		13	(C	C2)	
		(A1 = A2)		-	(B1 = B2)		(	C1 = C2)		

# 13.3 Analysis of Primary Endpoints

The desired sample size is 13 patients. We hope to demonstrate that ipilimumab monotherapy has significant clinical activity as a single agent, defined as an ORR of 40% or higher. The null hypothesis that the true ORR is 10% will be tested against a one-sided alternative (ORR 40%). The null hypothesis will be rejected if 4 or more patients of the 13 patients tested achieve an objective response. This design yields a type 1 error rate of 0.034 (one-sided) and a power of 0.83. Analysis of re-induction with ipilimumab + nivolumab among ipilimumab non-responders will be descriptive in nature.

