# 13.5.2 Evaluation of the Primary Efficacy Endpoint

The primary analysis will be performed on all evaluable patients.

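### Does Section 13.3 promise to demonstrate an ORR of 40% while testing only whether it exceeds 10%?

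*Combined protocol and SAP*

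**What the plan says.** Section 13.3 gives the whole design in one paragraph. It sets the size ("The desired sample size is 13 patients") and then the aim: "We hope to demonstrate that ipilimumab monotherapy has significant clinical activity as a single agent, defined as an ORR of 40% or higher". The next sentence makes 10% the null value of the true ORR and 40% the one-sided alternative. The decision rule is "The null hypothesis will be rejected if 4 or more patients of the 13 patients tested achieve an objective response", and its properties follow: "This design yields a type 1 error rate of 0.034 (one-sided) and a power of 0.83". There is no second confirmatory test, since "Analysis of re-induction with ipilimumab + nivolumab among ipilimumab non-responders will be descriptive in nature".

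Other sections touch the point only indirectly. The introduction to Section 13 is general: "The trial is designed to assess the efficacy of ipilimumab with or without nivolumab in patients with relapsed/refractory Hodgkin lymphoma". Section 13.5.2 names the analysis set: "The primary analysis will be performed on all evaluable patients". Section 1.2 frames the primary objective as estimating the monotherapy ORR. Section 13.1 also lists best ORR after ipilimumab monotherapy among the secondary endpoints, and Section 13.4 plans 95% confidence intervals for every secondary endpoint.

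**The concern.** The aim sentence attaches a definition to significant activity, and the definition is an ORR of at least 40%. The test that follows can exclude only 10%, and no interval bound, observed-rate threshold or second test is tied to 40%. A reader could take a positive test as proof of the defined activity when it is proof of something weaker.

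The awkward results are 4 and 5 responders. The null is rejected, yet the observed rate is below 40%. If the plan really held two standards, the authors of an open-label, single-arm report could choose after seeing the data whether to lead with activity shown or with target missed. These results are not rare, so the question deserves a check.

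**Working it through.** **Inputs, all from Section 13.3:** n = 13; reject if X ≥ 4; null rate 0.10; alternative rate 0.40; stated one-sided type 1 error 0.034; stated power 0.83. X is binomial(13, p), assuming all 13 patients are evaluable.

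**1. Reproduce the plan's figures.** P(X ≥ 4 | p) = 1 − Σ(k=0..3) C(13,k) pᵏ(1−p)¹³⁻ᵏ.

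- At p = 0.10: 1 − (0.2542 + 0.3672 + 0.2448 + 0.0997) = 0.0342 after carrying full precision. Stated: 0.034.
- At p = 0.40: 1 − (0.0013 + 0.0113 + 0.0453 + 0.1107) = 0.8314. Stated: 0.83.

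Both agree.

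**2. Size of the apparent conflict.** Observed rates are 4/13 = 30.8%, 5/13 = 38.5% and 6/13 = 46.2%, so 6 is the first count at or above 40%.

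| True ORR | P(X = 4) + P(X = 5) | P(X ≥ 4) | Share of positive results |
|---|---|---|---|
| 40% | 0.1845 + 0.2214 = 0.406 | 0.831 | 0.406/0.831 = 49% |
| 30% | 0.2337 + 0.1803 = 0.414 | 0.579 | 0.414/0.579 = 71% |

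**3. Which role for 40% fits the stated figures?** There are three candidate readings.

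| Reading of 40% | Count needed | Type 1 error at 10% | Power at 40% |
|---|---|---|---|
| True rate at which power is computed | 4 | 0.034 | 0.83 |
| Threshold for the observed rate | 6 | 0.0009 | 0.426 |
| Rate to be excluded by an exact test at one-sided 0.05 | 9 | below 0.000001 | 0.032 |

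For the third reading, P(X ≥ 8 | 0.40) = 0.098 is too large and P(X ≥ 9 | 0.40) = 0.032 is the first tail below 0.05. Only the first reading gives the plan's cut-off, error rate and power.

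**4. Do 4 or 5 responders contradict a 40% target?** The expected count at a true 40% is 13 × 0.40 = 5.2, so 5 responders is close to what a drug exactly on target would deliver. Exact (Clopper–Pearson) limits are:

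| Result | Two-sided 95% interval | One-sided 95% lower limit |
|---|---|---|
| 4/13 | 9.1% to 61.4% | 11.3% |
| 5/13 | 13.9% to 68.4% | 16.6% |

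Both intervals include 40%. The data would neither establish that rate nor rule it out, and the reported interval makes this plain. At 4/13 the two-sided interval also reaches just below 10%, because its lower tail uses 0.025 while the test operates at 0.034. The one-sided limit agrees with the rejection.

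**5. Is an interval already planned?** Yes. The monotherapy ORR is a secondary endpoint in Section 13.1, and Section 13.4 gives all secondary endpoints a 95% interval. The method is not named; the figures above assume the exact one.

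**The case for a change.** The strongest case for a change rests on the word that turns 40% into a definition. A 10%/40% layout is conventional, but a plan that only wanted a power target could have called it one. This is the only statement in the statistical section of what counts as significant activity, and no section says what conclusion a rejection supports. The ambiguous results carry probability 0.41 even when the planning assumption is true, and the cure is two sentences that leave the design alone.

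Part of this stands. The sentence is loose, and taken literally a test of a 10% null cannot demonstrate 40%. The conflict does not stand. To say that 4/13 misses the definition is to hold an observed rate against a statement about the true rate; the sentence after the aim speaks of the true ORR and uses 40% as the alternative. The aim is worded as a hope, while the rule that follows it is a count. Positive results below the alternative rate arise in any design whose cut-off, as a proportion, lies below that rate, so the 49% and 71% describe ordinary behaviour. The 58% rejection rate at a true 30% is a correct rejection of 10%. The silence of the Section 13 introduction and of Section 13.5.2 also shows little, since neither is where a success criterion would be placed.

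**Conclusion.** No change follows, because rewording would gain nothing. Section 13.3 fixes one null, one cut-off, one error rate and one power. All are correct, and together they leave 40% a single workable role: the true ORR the investigators hope for and at which power is computed. With 4 or 5 responders the plan yields one test result (10% rejected), one estimate (30.8% or 38.5%) and an interval that includes 40%. A competent analyst would report that the ORR exceeds 10% and that 40% is neither shown nor excluded. That report is the same with or without an edited sentence.

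This rests on 13 evaluable patients, on the conventional reading of a null and alternative pair, and on the 95% intervals of Section 13.4 being applied to the monotherapy ORR as Section 13.1 implies. What remains is loose wording in a statement of aim, with no effect on sample size, cut-off, type 1 error (0.034), power (0.83) or data collection.

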# 13.4 Analysis of Secondary Endpoints

Secondary endpoints include, response assessments including ORR (defined as partial response and complete response), the duration of response (DOR) among patients who have achieved a PR or CR (defined as the time from first response to progression or last follow-up), progression free survival (PFS) (defined as the time from treatment start to progression, death or last follow-up, whichever comes first), and overall survival (OS) (defined as time from treatment start to death or last follow-up). The safety of study will be assessed as measured by: the rate of grade 3 or higher toxicity regardless of attribution, the rate of grade 3 or higher toxicity at least possibly related to study treatment, and the rate of grade 2 or higher toxicity at least probably related to study treatment.

For patients who respond to treatment (complete or partial response), duration of response will be calculated from the date of response to the date of progression of disease. Patients still responding at date of last follow-up will be censored. PFS will be calculated as the time from start of treatment to the date of progression, death or last follow-up. OS will be calculated as the time from the start of treatment to the date of death or last follow-up. OS, PFS and DOR will be calculated using Kaplan-Meier methodology. 95% confidence intervals will be calculated for all secondary endpoints.

Correlative studies analyzing tissue samples using MIF and/or MIBI and circulating tumor DNA using next-generation sequencing based platforms are exploratory in nature. This testing is not powered to detect associations, but rather is designed to generate hypothesis for future studies. Completion of correlative studies will depend upon sample collection and budget considerations.

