# 10.3 Required at Progression or Treatment Discontinuation and Follow-Up

- Medication review, physical exam, vital signs, ECOG performance status (see Appendix A)
- Toxicity assessment
- CBC with manual differential, blood chemistries including complete metabolic panel, phosphorus, magnesium, uric acid, LDH, TSH, creatinine kinase, lipase, triglycerides. Urine studies to include a urine dipstick for blood and protein and if positive a microscopic urinalysis and 24-hour urine collection (for protein).
- Peripheral blood sample for biomarker studies at the time of progression (if feasible)
- Core-needle tumor biopsy at the time of progression (optional)
- Tumor restaging will be performed for patients in long-term follow-up who remain in remission. Patients who progress or receive other therapy for their lymphoma (for example, consolidation with transplantation or an alternative treatment) will only be followed for relapse and survival). Surveillance imaging will consist of PET/CT scans (including neck, chest, abdomen/pelvis) every 24 weeks for up to 2 years after initiation of study therapy.

DF/HCC Protocol #: 21-204 Protocol version date: v8/06 September 2023

• Patients in remission will be followed every 3 months for 2 years, then every 6 months for 3 years. Patients who progress or receive other therapy (for example consolidation with transplantation or an alternative treatment) will only be followed for relapse and survival.

• After 5 years of active follow up (for patients who remain in remission and do not receive additional treatment), patients will be followed only for relapse and survival with follow up by phone call with the patient or the local physician every 6 months for up to 5 years.

	Table 7 - Study Calendar											
	Baseline	Сус	ele 1ª	Cycle 2	Cycle 3	Cycle 4	Re- induction cycles 1-4 b	Maintenance Cycles c		ЕОТ	Follow- Up d, j	EDC Timepoints
	Day-28 to Day 0	Day 1	Day 14- 21	Day 1	Day 1	Day 1	Day 1	Day 1	Day 43	4-12 weeks from last study treatment		
					±3	days				± 7 days	±2 weeks	
Ipilimumab		X		X	X	X	(X)	X				Day 1 of induction and re-induction cycles and each maintenance cycle
Nivolumab							(X)					Day 1 of re- induction cycles
Informed consent	X											N/A
Demographics	X											Baseline
Medical history	X											Baseline
B-HCG e	X	X		X	X	X						Baseline
Urinalysis Hepatitis B and	X											Baseline
C serologies f	X											Baseline

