PT/PTT/INR EKG	X X											Baseline
Concurrent Medications	X	X		X						 	X	Baseline N/A
Physical exam	X	X		X	X	X	(X)	X	X	X	X	At each study visit
Vital signs	X	X		X	X	X	(X)	X	X	X	X	At each study visit
Height	X											Baseline
Weight	X	X		X	X	X	(X)	X				Baseline, day

												1 induction and re- induction cycles and day 1 of each maintenance cycle
Performance status (Appendix A)	X	X		X	X	X	(X)	X	X	X	X	A each study visit
CBC w/diff, serum chemistry g	X	X		X	X	X	(X)	X	X	X	X	At each study visit g
TSH, creatinine kinase, lipase, triglycerides, urine dipstick for blood and protein h	Х	X		X	X	X	(X)	X	X	X	X	At each study visit h
Cheek swab/saliva sample		X										On Cycle 1 Day1
Peripheral blood collection for biomarker studies i		X		X	X		(X)	Xi	X	X		See footnote
Tumor biopsies k	$X^k$		(X) k							(X) k		See footnote
Radiologic Evaluation 	X						(X)	$X^{l}$		X	X	See footnote
Adverse Event Evaluation			X	XX								

a: Cycles 1-4 are 21 days

b: Patients who achieve an objective response after 4 cycles of ipilimumab therapy will proceed to maintenance ipilimumab treatment. Ipilimumab non-responders (who are clinically stable) will receive re-induction with ipilimumab and nivolumab.

c: Maintenance cycles are 12 weeks (84 days). (see section 5.1)

d: Follow-up evaluation. Patients will continue on treatment until disease progression, withdrawal of consent, adverse events preventing additional therapy, or completion of study therapy. After completing treatment, patients will have every 3-month visits for 2 years or until progressive disease, then every 6-month visits for 3 years. Survival follow-up will then continue to be captured every 6 months for 5 years or until participant withdrawal, death, or removal from study. Patient who receive subsequent anti-cancer therapy will be followed for relapse and survival (but will not require active follow-up and surveillance imaging on trial).

e: Pregnancy testing at screening and on D1 of each cycle (for women of childbearing age only)

- f: Consisting at a minimum of hepatitis C antibody, hepatitis B surface antigen and hepatitis B core antibody.
- g: See Sections 10.1 and 10.2. All tests will be required at screening.
- h: See Sections 10.1 and 10.2.
- i: Peripheral blood sample(s) will be collected for correlative studies per section 9
- i: See Section 10.3.

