## 11.1.1 Duration of Response

Duration of overall response: The duration of overall response is measured from the time measurement criteria are met for CR or PR (whichever is first recorded) until the first date that recurrent or progressive disease is objectively documented (taking as reference for progressive disease the smallest measurements recorded since the treatment started, or death due to any cause. Participants without events reported are censored at the last disease evaluation).

Duration of overall complete response: The duration of overall CR is measured from the time measurement criteria are first met for CR until the first date that progressive disease is objectively documented, or death due to any cause. Participants without events reported are censored at the last disease evaluation.

Duration of stable disease: Stable disease is measured from the start of the treatment until the criteria for progression are met, taking as reference the smallest measurements recorded since the treatment started, including the baseline measurements.

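### Sections 11.1 and 13.4 define DOR and PFS differently (death as a DOR event, censoring date, time origin), and neither is given precedence

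*Combined protocol and SAP*

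**What the plan says.** **DOR.** Both sections start the clock at first response. Section 11.1.1 ends it at recurrence or progression "or death due to any cause. Participants without events reported are censored at the last disease evaluation". Section 13.4, which also holds the Kaplan-Meier instruction, states DOR twice. Once it is "defined as the time from first response to progression or last follow-up"; then "duration of response will be calculated from the date of response to the date of progression of disease". It adds that patients still in response at last follow-up are censored. Neither statement mentions death.

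**PFS.** Section 11.1.2 uses "time from randomization (or registration) to the earlier of progression or death due to any cause" and adds: "Participants alive without disease progression are censored at date of last disease evaluation". Section 13.4 has PFS "defined as the time from treatment start to progression, death or last follow-up, whichever comes first". Death is a PFS event in both.

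**OS.** The origin differs in the same way: randomization or registration in 11.1.2, treatment start in 13.4.

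**Schedules that set the two censoring dates.** Under footnote d of the study calendar (Table 7), after treatment "patients will have every 3-month visits for 2 years or until progressive disease, then every 6-month visits for 3 years". Section 10.3 sets surveillance imaging "every 24 weeks for up to 2 years after initiation of study therapy". Section 5 (text under Figure 1), Section 10.2 and footnote l of Table 7 instead continue 24-weekly scans after the end-of-treatment assessment and give no end date. Section 5.7 allows follow-up to 10 years after removal from therapy.

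No text says which set of definitions governs the analysis, and neither section refers to the other.

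**The concern.** Section 1.3 lists DOR, PFS and OS as secondary objectives, and 13.4 promises 95% confidence intervals for all secondary endpoints. An analyst programming from the statistics section would use a DOR rule that omits death and a censoring date that may fall after the last scan. An analyst using Section 11.1 would do neither.

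The two main differences push in the same direction. Censoring a death removes a drop from the Kaplan-Meier curve. Later censoring keeps patients in the risk set, so each later event causes a smaller drop. If the choice is left until the data are seen, the more favourable version is available and the choice would look selective. A death in remission is a foreseeable case here: Section 6.8 has a study-wide rule for treatment-related grade 5 events.

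**Working it through.** **The plan's own figure.** The only design calculation is for the primary endpoint (Section 13.3: at least 4 responses in 13, ORR 10% versus 40%).

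- α = P(X ≥ 4 | n = 13, p = 0.10) = 0.0342; stated 0.034.
- Power = P(X ≥ 4 | n = 13, p = 0.40) = 0.8314; stated 0.83.

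Both reproduce, and neither depends on how DOR or PFS is defined. No design figure is given for DOR or PFS, so the rest compares the texts and uses assumed data.

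**Side by side.**

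| Item | Section 11.1 | Section 13.4 |
|---|---|---|
| DOR events | progression or death | progression only is named |
| DOR and PFS censoring | last disease evaluation | last follow-up |
| PFS and OS origin | randomization or registration | treatment start |
| PFS events | progression or death | progression or death |

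**Death rule for DOR (assumed data).** The expected number of responders at the design ORR is 0.40 × 13 = 5.2, so about 5. Kaplan-Meier: S(t) = ∏(1 − d/n), with d events among n at risk. The 13.4 values treat the death as censored, which is the literal reading.

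One death in remission as the first event:

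| Responders | 11.1.1 | 13.4, literal |
|---|---|---|
| 4 | 3/4 = 75% | 100% |
| 5 | 4/5 = 80% | 100% |
| 6 | 5/6 = 83% | 100% |

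Five responders, sequence death, progression, progression, two censored:

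- 11.1.1: 4/5 = 0.80; × 3/4 = 0.60; × 2/3 = 0.40.
- 13.4: 1.00; × 3/4 = 0.75; × 2/3 = 0.50.

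A second assumed data set has progressions at 3 and 9 months, one death in response at 6 months and all others censored at 12 months. With 4 responders, median DOR is 6 months if the death counts and 9 months if it is censored. With 5 or 6 responders it is 9 months versus not reached.

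**Censoring date.** Take visits at 3, 6, …, 24 and then 30, 36, …, 60 months, and scans at 24, 48, 72, … weeks from the same date (assumed). One month is 30.4375/7 = 4.348 weeks. The gap is the visit week minus the week of the latest scan:

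- Month 6: 26.1 − 24 = 2.1 weeks, the smallest.
- Month 21: 91.3 − 72 = 19.3 weeks, the largest in the first 2 years.
- Month 60: 260.9 − 240 = 20.9 weeks, the largest overall.
- Month 3 comes before the first scan, 13.0 weeks from the origin.

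The gap is therefore about 2 to 21 weeks if scans continue throughout. Under the imaging limit in 10.3, scans stop about week 104. That is before the end-of-treatment assessment at weeks 112–120 for patients who complete therapy, and the gap could then run to years.

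**Time origin.** Registration precedes treatment, so starting at treatment shortens PFS and OS. Section 4.3 asks outside sites to begin therapy within 5 days of registration: 5/30.4375 = 0.16 months. Section 4.1 gives no limit for DF/HCC sites.

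**The case against.** The strongest reply is that 13.4 is silent on death in response rather than in conflict with 11.1.1. Its censoring sentence covers patients still responding, which does not naturally describe someone who has died, so 11.1.1 could be read as filling the gap. Being still responding at last follow-up might likewise imply that disease was assessed at that time. A careful analyst could reach the 11.1 rules this way. But nothing directs the analyst to 11.1, and 13.4 names death for PFS while omitting it for DOR in the same paragraphs. For PFS the two censoring dates plainly differ.

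The 2-to-21-week gap is one scenario. If visits run from the last dose and scans from an assessment 4 to 12 weeks later, the gap depends on the offset. For the month-12 visit (week 52.2), an offset of 4 weeks puts a scan at week 52 (gap 0.2 weeks). An offset of 5 weeks puts the latest scan at week 29 (gap 23.2 weeks). The dates still differ.

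The origin point is minor. In a trial without randomization the phrase in 11.1.2 reduces to registration, and the 28-day screening window in Section 10.1 puts some indirect limit on the delay.

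One further point stands but is separate. Section 1.3 asks for PFS in the re-induction group, many of whom will enter after progression on ipilimumab. Neither section says which treatment start applies to them.

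Finally, these are secondary estimates with no stated test in 13 patients, and the death example is hypothetical. That limits the importance of the conflict but does not remove it.

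**Conclusion.** The concern holds. The DOR event rule, the DOR and PFS censoring date, and the PFS and OS origin all differ between Sections 11.1 and 13.4, and the plan does not say which applies. Followed literally, 13.4's DOR event rule and its censoring date can only leave the DOR and PFS curves unchanged or raise them.

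The size depends on data not yet seen. With 4 to 6 responders, one death in remission as the first event moves DOR by 17 to 25 percentage points at that time (100 − 83 to 100 − 75). After two later progressions among 5 responders the difference is 10 points (50 − 40). It is zero if no responder dies without progression and last follow-up coincides with a disease evaluation. The origin difference is small and works the other way.

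The primary ORR test, sample size, α and power are untouched. The point should be corrected before analysis, but it does not threaten the trial's main conclusion.

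**What to change.** - **Section 13.4:** define the event for both DOR and PFS as progression or death from any cause, and censor event-free patients at the last disease evaluation, as 11.1.1 and 11.1.2 already do.
- **Section 11.1.2:** replace the reference to randomization or registration with treatment start, as in 13.4, for PFS and OS. Apply the same origin to time to progression, which carries the same phrase.
- **One source:** keep each full definition in one section and cross-refer from the other.
- **Imaging schedule:** reconcile the duration of surveillance imaging between Section 10.3 and Section 5, Section 10.2 and footnote l of Table 7, since it determines the last disease evaluation.
- **While editing:** state which treatment start applies to PFS in the re-induction group. This is a separate gap, but it sits in the same sentences.

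The cost is wording. The definitions need no new data, and N, α and power do not change. Reported DOR and PFS may be somewhat less favourable than under a literal reading of 13.4.
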